## **Data Entry and Confidentiality**

Data are anonymized, coded, and entered into a secure electronic database. All identifying

information is removed to maintain participant confidentiality. Only authorized members of the research team have access to the data.

# **Statistical Analysis**

- **Descriptive Statistics**: Descriptive statistics will summarize the demographic characteristics of participants and provide baseline data on grief and depressive symptoms for each group. Mean, standard deviation, and percentage values will be reported for categorical and continuous variables.
- **Primary Analysis**: Repeated measures ANOVA will be conducted to examine the effects of each intervention (EH and CBT) across the three time points (baseline, midpoint, post-intervention) on the primary outcome measure (PGS) and secondary outcome measure (BDI). This analysis allows for the comparison of changes in grief and depressive symptoms within and between groups over time.
- Post-Hoc Comparisons: Following significant ANOVA results, post-hoc pairwise
  comparisons will be conducted to determine specific differences between time points and
  intervention groups. This analysis will help identify any statistically significant improvements
  in grief and depressive symptoms from baseline to midpoint and from midpoint to postintervention.
- Effect Size Calculation: Cohen's d will be calculated to quantify the effect size of EH and CBT interventions on grief and depressive symptoms, providing insights into the practical significance of each therapeutic approach.

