## **Objective:**

The objective of this study is to compare the efficacy of Ericksonian Hypnotherapy (EH) and Cognitive Behavioral Therapy (CBT) in reducing prolonged grief symptoms among university students in Istanbul. Prolonged grief is characterized by an intense longing and emotional distress related to a loss that extends beyond typical bereavement, impacting mental health and daily functioning. By evaluating the effectiveness of EH, a flexible therapeutic approach using indirect suggestion and metaphoric techniques, against the structured approach of CBT, the study aims to identify a potentially effective and culturally adaptable intervention for young adults coping with prolonged grief.

This study will address the following primary research question:

• Does Ericksonian Hypnotherapy provide a more effective reduction in prolonged grief symptoms than Cognitive Behavioral Therapy among university students?

Secondary research questions include:

- How do these interventions affect depressive symptoms associated with prolonged grief?
- Can EH offer a culturally sensitive therapeutic alternative in diverse university settings?

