## 2. Study Design

# **Type:**

This is a randomized controlled trial (RCT) employing an expertise-based parallel group design to evaluate the effects of Ericksonian Hypnotherapy (EH) and Cognitive Behavioral Therapy (CBT) on prolonged grief symptoms among university students. Participants are randomly assigned to one of three groups: (1) Ericksonian Hypnotherapy, (2) Cognitive Behavioral Therapy, or (3) a Waitlist Control group.

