# 5. Outcome Measures

#### **Primary Outcome Measure**

• **Prolonged Grief Scale (PGS)**: The primary outcome measure is the Prolonged Grief Scale (PGS), a validated tool for assessing the intensity and severity of prolonged grief symptoms. The scale consists of 13 items measuring symptoms such as persistent yearning for the deceased, emotional pain related to the loss, and difficulty accepting the reality of the death. Each item is rated on a Likert scale, providing a quantifiable grief score for each participant. This scale is administered at baseline, midpoint (after the fourth session), and post-intervention (after the eighth session) to track changes in grief severity over time. Higher scores indicate more intense grief symptoms.

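### The primary question is EH versus CBT on PGS, but the primary analysis is an omnibus repeated measures ANOVA that does not make that contrast the deciding test

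*Combined protocol and SAP*

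**What the plan says.** The Objective section asks one primary question: "Does Ericksonian Hypnotherapy provide a more effective reduction in prolonged grief symptoms than Cognitive Behavioral Therapy among university students". Section 2 (Type) has three arms: "Participants are randomly assigned to one of three groups". Under Primary Outcome Measure, the PGS is "administered at baseline, midpoint (after the fourth session), and post-intervention (after the eighth session) to track changes in grief severity over time"; none of these visits is called primary.

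Under Statistical Analysis, the primary analysis reads: "Repeated measures ANOVA will be conducted to examine the effects of each intervention (EH and CBT) across the three time points". It covers both PGS and BDI, and the plan adds: "This analysis allows for the comparison of changes in grief and depressive symptoms within and between groups over time". It does not say whether the group, time or interaction effect decides the trial. Baseline enters as a level of time, not as a covariate. The next step begins "Following significant ANOVA results, post-hoc pairwise" comparisons, with no multiplicity method. The changes it spells out are those "in grief and depressive symptoms from baseline to midpoint and from midpoint to postintervention". Cohen's d "will be calculated to quantify the effect size of EH and CBT interventions on grief and depressive symptoms", with no comparator given.

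Other text bears on how to read this. Data Collection Schedule places the baseline PGS before randomisation. Data Collection Process lists only EH and CBT at midpoint, while the Schedule has no such limit. Handling Missing Data keeps everyone in the allocated arm and plans multiple imputation.

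**The concern.** The text supports two models.

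- **Three arms** (section 2, and the commitment to analyse everyone as allocated). A significant time effect or interaction can then arise with no EH–CBT difference at all, and the primary question is reached only post hoc.
- **EH and CBT only** (the two arms named in the primary analysis and at midpoint). The group-by-time interaction then does test EH versus CBT, but with 2 degrees of freedom and without using baseline as a covariate.

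At stake is whether the headline result answers the question asked, whether the EH–CBT conclusion rests on one test fixed in advance, and some power in a trial with 13 per arm. Cohen's d could also mislead if it is computed within arm.

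**Working it through.** **Inputs.** From the plan: 13 per arm, 39 in total, three visits. The plan gives no alpha, target power, SD, correlation or numeric effect (the Sample Size text says only that the effect is moderate), so it has no power figure to reproduce. Assumed here: two-sided 0.05, SD 1, equal correlation ρ between visits, no dropout. Unless stated otherwise, change is linear with EH −1.0, CBT −0.5 and waitlist 0 at post-intervention, a true EH–CBT difference of 0.5 SD. Percentages are from simulation (at least 20,000 trials per scenario) and are given for ρ = 0.5 / 0.7.

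**1. Does a significant ANOVA answer the question?** Set EH = CBT.

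- Both at −1.0, waitlist 0: the three-arm interaction is significant in about 61% / 85%.
- Same 0.8 SD improvement in every arm: the time effect is significant in over 99% (three arms) or 95% / 99.7% (two arms).

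**2. Standard errors of the EH–CBT estimate.**

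- Baseline-adjusted (ANCOVA): √[(2/13)(1 − ρ²)] = √(0.1538 × 0.75) = 0.340 at ρ = 0.5, and √(0.1538 × 0.51) = 0.280 at ρ = 0.7.
- Change score: √[(2/13) × 2(1 − ρ)] = √(0.1538 × 1.0) = 0.392, and √(0.1538 × 0.6) = 0.304.
- Variance ratio: (1 − ρ²)/[2(1 − ρ)] = (1 + ρ)/2 = 0.75, 0.85 and 0.95 at ρ = 0.5, 0.7 and 0.9. The gain over a change score therefore fades as ρ rises.

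Noncentral t for ANCOVA, with a small allowance for chance baseline imbalance, gives 29.2% / 40.2% (35 df, three-arm model) and 28.1% / 38.7% (23 df, two-arm).

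**3. Power for 0.5 SD.**

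| Test of EH versus CBT | Power | ANCOVA gain (points) |
|---|---|---|
| ANCOVA, three-arm model | 29–30% / 40% | – |
| ANCOVA, two arms | 28% / 39% | – |
| Two-arm interaction F-test | 18% / 28% | 10–11 |
| Change test after a significant three-arm interaction | 18% / 32% | 11 / 8 |
| Same, waitlist also improves by 0.25 SD | 15% / 27% | about 14 |
| Change test after a significant two-arm interaction | 15% / 25% | about 14 |
| Change test after any significant effect | 22–24% / 35–37% | 4–7 / 2–5 |

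At ρ = 0.9 the last comparison is level (78–80% for both). The time course matters too. If the full 0.5 SD is already present at midpoint, the two-arm interaction has 23% / 36% / 52% at ρ = 0.5 / 0.7 / 0.8, against 28% / 38% / 52% for ANCOVA: gains of 5, 2 and 0 points.

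**4. False EH–CBT findings when EH = CBT.**

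| Procedure | At least one false finding |
|---|---|
| Three between-visit changes, unadjusted, after any significant effect; 0.8 SD trend in all arms | about 12% |
| Same, only the two successive changes | about 9% |
| Three changes, unadjusted, after a significant three-arm interaction; both therapies beat waitlist | 11–12% |
| Three changes with Bonferroni, after any significant effect | 4.4–4.6% |
| Three changes, unadjusted, after any significant effect; no trend | about 4% (three arms), 6% (two arms) |
| Three changes, unadjusted, after a significant three-arm interaction; equal trend | 3% |
| Three changes, unadjusted, after a significant two-arm interaction | 5% |
| Single ANCOVA contrast | 5% |

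**5. Cohen's d.** With the same 0.8 SD trend in every arm, a within-arm pre–post d averages 0.83 / 0.84, while the between-arm d averages 0.

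**6. What the contrast cannot do.** With 35 df, 80% power needs a difference of about 0.99 / 0.82 SD. The 95% CI half-width is 2.03 × 0.340 = 0.69, or 2.03 × 0.280 = 0.57 SD.

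**The case against.** The plan expressly allows for comparison between groups over time, and repeated measures ANOVA is a valid test of change. If only EH and CBT enter, its interaction tests the primary question at 5%, and the issue is efficiency. That stands.

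A reader might infer that any visit could be picked after the fact. The documents do not support that fully. Data Collection Process treats midpoint as interim and preliminary and ties the final assessment to the overall effect of treatment; Data Collection Schedule links the final assessment to comparing symptoms before and after treatment. These point to baseline-to-post, though neither formally names a primary visit.

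A reader might also infer that the false-positive rate is generally well above 5%. It is not. The figure of about 12% needs two things together: several EH–CBT changes tested without adjustment, and a preliminary test opened by a time trend or by a treatment-versus-waitlist effect. The plan is silent on adjustment; it does not say the tests will be unadjusted. The two successive changes it mentions are described as improvements, which reads more naturally as change within arms than as two EH–CBT tests.

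Finally, the power gain rests on inputs the plan does not supply. Linear change favours a post-intervention contrast. With an early, sustained difference the gain shrinks to nothing at ρ = 0.8 and can reverse at higher correlation. So the contrast is not more powerful in every case.

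What remains is that no deciding effect, contrast or multiplicity rule is stated, and that under the three-arm reading the omnibus result may not concern EH versus CBT.

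**Conclusion.** The point holds as a matter of matching the primary test to the primary question. It does not show that the ANOVA is invalid or that the plan cannot compare EH with CBT.

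Under the three-arm reading, the omnibus result can be significant in most trials with EH and CBT equal (61% / 85% in the scenario assumed). Under the two-arm reading, the interaction is valid but usually less efficient. For a 0.5 SD difference, the gain from a direct adjusted contrast over change-based or interaction tests is roughly 0 to 11 points. It reaches about 14 if the waitlist also improves, or if a two-arm interaction and a follow-up change test must both succeed. It is smallest at high correlation or when the full difference is present by midpoint. All of this assumes 13 per arm, two-sided 0.05, equal correlation between visits and no dropout.

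The change should be made before outcome data are analysed. It will not make the trial adequately powered: about 28–40% for 0.5 SD at ρ 0.5–0.7.

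**What to change.** In the Statistical Analysis section:

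- **Primary test:** the EH minus CBT difference in post-intervention PGS, adjusted for baseline PGS, by ANCOVA or an equivalent mixed model with arm-by-visit and baseline-by-visit terms. Report the 95% CI, test once at two-sided 0.05, and do not make it conditional on an omnibus test.
- **Secondary:** EH versus waitlist and CBT versus waitlist, Holm-adjusted; BDI by the same model.
- **Effect size:** Cohen's d from the between-arm adjusted difference.
- **Supportive:** the repeated measures ANOVA, the midpoint contrast and within-arm changes, stating which arms enter and which effect is read.
- **Reporting:** lead with the confidence interval, because power is low.

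Naming post-intervention as the primary visit is a proposal, consistent with the data collection text. The contrast does not depend on whether the waitlist has a midpoint visit, and as a single estimate it pools directly over the imputed datasets.

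Cost: wording only, with no new data. The adjustment uses one model degree of freedom. In the ANCOVA form, midpoint PGS leaves the primary test; the mixed model retains it. Omnibus and within-arm significance claims lose primary status.

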## **Handling Missing Data**

For any missing data due to participant non-completion of assessments, multiple imputation methods will be applied to reduce bias. The study will follow an intent-to-treat approach, analyzing all participants as randomized to their initial groups to maintain the study's validity and statistical power.

#### 7. Ethical Considerations

## **Ethics Approval and Compliance**

This study has received ethical approval from the Institutional Review Board of Istanbul Nişantaşı University (Approval No: 2023/2). All study procedures comply with ethical guidelines for research involving human participants, as outlined in the Declaration of Helsinki. The study is registered on ClinicalTrials.gov (Registration No: NCT06398886), ensuring transparency and adherence to clinical trial regulations.

## **Informed Consent**

Informed consent is obtained from all participants prior to their enrollment in the study. The consent form details the study's purpose, procedures, potential risks, and benefits. Participants are informed of their voluntary participation status, confidentiality safeguards, and their right to withdraw from the study at any time without consequences.

## **Confidentiality and Data Protection**

Participant confidentiality is rigorously protected. All data collected are anonymized and stored securely, with access restricted to authorized research team members only. Unique identification codes are assigned to participants to maintain privacy, and all identifying information is removed from the dataset.

# **Risk Management**

This study involves minimal risk, primarily associated with emotional discomfort that may arise during discussions of grief. Therapists conducting the sessions are trained professionals, capable of identifying signs of distress and providing immediate support or referrals if necessary. Participants are also informed of this possibility during the consent process and encouraged to communicate any concerns during the sessions.

# **Post-Study Support for Control Group**

Participants assigned to the waitlist control group do not receive therapeutic intervention during the study period. Upon study completion, these participants are provided with information on local grief counseling resources to ensure they have access to support if desired.

## **Data Availability Statement**

All anonymized data supporting the findings of this study will be made publicly available upon request. Data will be accessible in line with open science principles while maintaining participant confidentiality.
